4 STUDY DESIGN AND ENDPOINTS

4.1 DESCRIPTION OF THE STUDY DESIGN

Trial Design

The trial is an open-label, single arm phase II study to be conducted only at the Moffitt Cancer Center. Anticipated accrual will be 25 subjects. One of the secondary endpoint of this study is reconstitution of immune function, using response to pneumococcal vaccination as a clinical surrogate representation of global immune function. The study is designed to test the null hypothesis that, in high risk CLL (defined as presence of del17p or TP53, del11q or ATM mutation, unmutated IGVH or mutated IGVH with 3.21 phenotype) patients who do not require treatment of CLL and receive PD-1:PD-L1 blockade along with ibrutinib, challenge with the 7-valent pneumococcal vaccine will elicit an immunologic response <40%, defined as the generation of detectable antibody responses to >6 antigens. Our specified alternative hypothesis is that vaccination in the context of PD-1 blockade and ibrutinib will elicit an immunologic response >60% with 90% power.

Overall treatment Schema: All intravenous treatments will be administered at the outpatient Moffitt Cancer Center Infusion Center. The patients will receive a combination of IV pembrolizumab (anti-PD1) and oral ibrutinib according to the scheduled depicted in Figure 1. Briefly, patients will receive pembrolizumab on a 3-week interval schedule for a total of at least 51 weeks (it could be extended for up to 2 years if clinical benefit per investigator); starting with week 6, patients will additionally start daily oral ibrutinib which will be continued through 54 weeks of ibrutinib therapy. The rationale of starting pembrolizumab first is to avoid overlapping toxicity of ibrutinib and the anti-PD1 antibody.

Biomarker Research

Immune Monitoring Laboratory Correlates:

1. Global Immune function will be assessed in terms of serum cytokine patterns. Patient sera will be evaluated by flow cytometric means using cytokine bead arrays to measure serum cytokine levels quantitatively. The cytokine panel will include IFN- γ , TNF- α , IL-2, IL-4, IL-10, IL-6, IL-17A, allowing discrimination between TH1, TH2, and TH17 profiles.
2. T cell function will be assessed for changes in multiple characteristics including memory formation, TH-polarity, markers of exhaustion, and activation via flow cytometric analysis. Naïve and memory subpopulations will be defined according to expression of CD45RA, CD62L, CCR5 and CCR7. TH-polarization, including TH1, TH2, TH17 and TReg subsets, will be determined by intracellular cytokine and FoxP3 profiles. Changes in T cell exhaustion phenotype will be tracked in terms of surface expression of several well-defined markers, including CD160, CD200R, CD244, CD272, CD274, CD279, as well as the intracellular markers Lag3 and Tim3. Alterations in cellular activation will be measured in terms of phosphorylation of critical T cell signaling pathways, STAT 1, 3 and 5, as well as by surface expression of CD107a, correlating to secretory/cytotoxic activity.
3. Humoral immunity will be monitored in terms of quantitative serum immunoglobulin levels as well as IgG subtyping by ELISA assay. FcR subtype utilization patterns will also be evaluated by flow cytometric means to identify potential alterations in cellular interpretation of antibody-mediated signaling.
4. Evaluation of MRD by 4-color flow cytometry. It will be performed in patients who achieved CR and PR per iwCLL criteria. If CBC with differential demonstrates the normalization of WBC to normal limits with no evidence of lymphocytosis, a peripheral blood sample will be obtained (within 14 days) to determine the MRD status of the CLL in peripheral blood by multiparameter flow cytometry. If MRD is negative, a confirmation of MRD status in the bone marrow will be performed at the discretion of the investigator.
5. Peripheral blood to collect DNA and RNA will be stored for future assessments.

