Pembrolizumab (MK-3475) is a potent and highly selective humanized monoclonal antibody (mAb) of the IgG4/kappa isotype designed to directly block the interaction between PD-1 and its ligands, PD-L1 and PD-L2. Pembrolizumab is currently FDA approved for the first-line treatment of metastatic wild type EGFR and ALK non-small lung cancer (NSCLC) that express high PD-L1 expression [Tumor Proportion Score (TPS) \geq 50%], for metastatic NSCLC with progression on or after platinum containing chemotherapy with TPS \geq 1% expression of PD-L1, for metastatic EGFR or ALK rearrangement NSCLC with progression after EGFR and/or ALK inhibitors, for unresectable or metastatic melanoma and for recurrent or metastatic head and neck squamous cell carcinoma (HNSCC) after progression to platinum-containing chemotherapy.

The importance of intact immune surveillance in controlling outgrowth of neoplastic transformation has been known for decades [15, 35]. Accumulating evidence shows a correlation between tumor-infiltrating lymphocytes (TILs) in cancer tissue and favorable prognosis in various malignancies [16-19, 21]. In particular, the presence of CD8+ T-cells and the ratio of CD8+ effector T-cells / FoxP3+

regulatory T-cells seems to correlate with improved prognosis and long-term survival in many solid tumors[36].

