- **Immunogenicity:** As with all therapeutic proteins, there is the potential for immunogenicity. Trough levels of pembrolizumab interfere with the electrochemiluminescent (ECL) assay results; therefore, a subset analysis was performed in the patients with a concentration of pembrolizumab below the drug tolerance level of the anti-product antibody assay. In clinical studies in patients treated with pembrolizumab at a dose of 2 mg/kg every 3 weeks, 200 mg every 3 weeks, or 10 mg/kg every two or three weeks, 26 (2.0%) of 1289 evaluable patients tested positive for treatment-emergent anti-pembrolizumab antibodies. Among the 26 patients who tested positive for treatment emergent anti-pembrolizumab antibodies, only 4 patients were tested for neutralizing antibodies and one was positive. There was no evidence of an altered pharmacokinetic profile or increased infusion reactions with anti-pembrolizumab binding antibody development. The detection of antibody formation is highly dependent on the sensitivity and specificity of the assay. Additionally, the observed incidence of antibody (including neutralizing antibody) positivity in an assay may be influenced by several factors including assay methodology, sample handling, timing of sample collection, concomitant medications, and underlying disease. For these reasons, comparison of incidence of antibodies to pembrolizumab with the incidences of antibodies to other products may be misleading.

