3 OBJECTIVES AND PURPOSE

Objective:

This is designed as a phase II study intended to evaluate the impact of sequential overlapping treatment with PD-1 monoclonal antibody (mAb), pembrolizumab/MK-1375, followed by ibrutinib on endogenous immune function in previously untreated, high-risk CLL patients (defined as presence of del17p or TP53, del11q or ATM mutation, unmutated IGVH or mutated IGVH with 3.21 phenotype) with absolute lymphocyte count >20,000 but without meeting iwCLL criteria to start therapy.

Primary Objectives:

1. Assessment of the complete response (CR) of CLL to therapeutic intervention (defined per current iWCLL 2008 response criteria)
2. Time to response of CLL to therapeutic intervention (defined as time to achievement of response according to iWCLL 2008 criteria).

Secondary Objectives

1. Assessment of the overall response rate (ORR) [CR + PR] per iWCLL 2008 response criteria
2. Restoration of immune response as measured by:
 - a. Decreased markers of T-cell exhaustion
 - b. Increased of quantitative immunoglobulin levels and subtype
2. Safety and toxicity of the combination
3. Progression free survival (PFS)
4. 3. Incidence of Richter's transformation (defined as transformation of CLL into an aggressive lymphoid/histiocytic histology including well defined World Health Organization 2008 subtypes). Richter's transformation should be biopsy proven

Exploratory Objectives:

1. Alterations in T lymphocyte function, including changes in:
 - a. TH1:TH2 polarization, and TReg:TH17 distributions
 - b. Markers of T cell exhaustion and/or inhibition
 - c. Alterations in distribution of naïve vs. memory
 - d. Cellular activation and cell-mediated cytotoxic capacity
2. Alterations in B lymphocyte function, including changes in:
 - a. Serum anti-pneumococcal antibody titers in response to Prevnar vaccination
 - b. Quantitative serum immunoglobulin levels and subtyping
 - c. Fc-receptor (FcR) expression patterns
3. Alterations in global systemic cytokine patterns: Includes IFN- γ , TNF- α , IL-2, IL-4, IL-10, IL-6, IL-17A, allowing discrimination between TH1, TH2, and TH17 profiles (described in Section 4.2.2.2)

Hypothesis for Primary and Secondary Objectives:

The therapeutic combination of PD1:PDL1 blockade (PDB) and ibrutinib can improve the severe immune dysfunction classically associated with CLL, thereby improving disease-related morbidity and mortality in high-risk, previously untreated patients.

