6.1.2 FORMULATION, APPEARANCE, PACKAGING, AND LABELING

IBRUTINIB

Ibrutinib is an inhibitor of Bruton's tyrosine kinase (BTK). Ibrutinib is a small-molecule inhibitor of BTK. Ibrutinib forms a covalent bond with a cysteine residue in the BTK active site, leading to inhibition of BTK enzymatic activity. BTK is a signaling molecule of the B-cell antigen receptor (BCR) and cytokine receptor pathways. BTK's role in signaling through the B-cell surface receptors results in activation of pathways necessary for B-cell trafficking, chemotaxis, and adhesion. Nonclinical studies show that ibrutinib inhibits malignant B-cell proliferation and survival in vivo as well as cell migration and substrate adhesion in vitro. It is a white to off-white solid with the empirical formula C25H24N6O2 and a molecular weight 440.50. Ibrutinib is freely soluble in dimethyl sulfoxide, soluble in methanol and practically insoluble in water. Ibrutinib capsules for oral administration are supplied as white opaque capsules that contain 140 mg ibrutinib as the active ingredient. Each capsule also contains the following inactive ingredients: croscarmellose sodium, magnesium stearate, microcrystalline cellulose, sodium lauryl sulfate. The capsule shell contains gelatin, titanium dioxide and black ink. Each white opaque capsule is marked with "ibr 140 mg" in black ink. Clinical supplies will be affixed with a clinical label in accordance with regulatory requirements.

The white opaque 140 mg capsules marked with "ibr 140 mg" in black ink are available in white HDPE bottles with a child-resistant closure:

- 90 capsules per bottle: NDC 57962-140-09

PEMBROLIZUMAB

Pembrolizumab is a humanized monoclonal antibody that blocks the interaction between PD-1 and its ligands, PD-L1 and PD-L2. Pembrolizumab is an IgG4 kappa immunoglobulin with an approximate molecular weight of 149 kDa. Binding of the PD-1 ligands, PD-L1 and PD-L2, to the PD-1 receptor found on T cells, inhibits T cell proliferation and cytokine production. Upregulation of PD-1 ligands occur in some tumors and signaling through this pathway can contribute to inhibition of active T-cell immune surveillance of tumors. Pembrolizumab is a monoclonal antibody that binds to the PD-1 receptor and blocks its interaction with PD-L1 and PD-L2, releasing PD-1 pathway-mediated inhibition of the immune response, including the anti-tumor immune response. In syngeneic mouse tumor models, blocking PD-1 activity resulted in decreased tumor growth.

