7.1.13 Correlative Studies Blood Sampling

Blood samples will be collected pre-dose on Day 1, Week 6, Week 21, and end of ibrutinib therapy for immune testing per Schedule of Events. They will be performed at investigator's discretion if early study termination. For sampling requirements, see Section 7.2.

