7.2 RESEARCH BLOOD SPECIMEN PREPARATION, HANDLING, AND STORAGE

Blood samples for correlative studies will be collected at baseline (prior to first dose of study drug), at week 9, week 12, and end of ibrutinib treatment. Peripheral blood will be utilized with an estimated volume of 50 cc collected in five green top tubes.

1. Preparation of Samples

Whole blood samples in 5 green top tubes (10ml/tube) will be received in the laboratory of [name]. Plasma will be isolated by centrifugation of the green top tubes for 5min at 1500rpm and lymphocyte isolation will be performed using Ficol gradient isolation for the purpose of immune testing.

2. Sample Storage

For storage, plasma will be held in 1.5 ml aliquots and placed in a -20C freezer. Lymphocytes will be frozen using 90% FBS and 10% DMSO and placed in a -80C freezer for short term storage. Long term storage of lymphocytes will be conducted utilizing liquid nitrogen.

3. Long-Term Use of Samples

Any isolated plasma and lymphocytes will be stored for the duration of the trial utilizing the short term method above and will be tested per protocol parameters outlined in Section 4.1. With the subject's permission, any samples remaining at the end of the trial will be placed in long term storage for use in future research. If any subject does not agree, that subject's remaining samples will be destroyed at the final closure of the trial.

4. Procedure for Clinical Trial Staff

The following procedure is recommended to be used for collaboration with the Research Science Lab:

- a. Notify the Research lab at least 2 days prior to the collection, using the template below.
Email to [contact] and cc [contact]
Follow up with a phone message to [name].
- b. Prepare a plastic bag with 5 green top tubes (tubes obtained from [name] lab). Attach label to tubes with MCC #, subject MRN, and date of collection. Each bag will have a label attached with the MCC #, subject MRN, DOB, initials, date/time of collection. Label should have research lab contact information. ("Contact [name] or [contact] for pick-up").
- c. Deliver bag of tubes to the Blood Draw area the day prior to collection.

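### CD279 (PD-1), the receptor pembrolizumab binds, is listed as a T-cell exhaustion marker; if the staining antibody competes with bound drug, a fall in CD279 can appear without any change in the T cells.

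*Combined protocol and SAP*

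**What the plan says.** Sections 3 and 4.2.2 make "Decreased markers of T-cell exhaustion" one part of the secondary objective and endpoint on restoring the immune response. Section 4.1 (Biomarker Research) assesses "markers of exhaustion, and activation via flow cytometric analysis" and names eight exhaustion markers: "surface expression of several well-defined markers, including CD160, CD200R, CD244, CD272, CD274, CD279" on the surface, and Lag3 and Tim3 inside the cell. It names no antibody clone, occupancy control or interference check.

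Section 10.2.2 compares baseline with a sample at week 52 by paired t-test, or by Wilcoxon signed-rank test if normality fails. The test is one-sided at 0.05, with a stated detectable effect of 0.60 at 25 patients. It does not say which markers define exhaustion, how they are combined, or whether the level is adjusted for several markers.

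On the drug, 6.1.2 says "Pembrolizumab is a monoclonal antibody that binds to the PD-1 receptor and blocks its interaction with PD-L1 and PD-L2". The schedule of events (7.3.7, footnote 2) gives it every 3 weeks for 51 weeks. On sampling, 7.1.13 says "Blood samples will be collected pre-dose on Day 1, Week 6, Week 21, and end of ibrutinib therapy", and footnote 12 of 7.3.7 agrees, but 7.2 places the draws after baseline "at week 9, week 12, and end of ibrutinib treatment".

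**The concern.** The baseline sample is drawn before the first infusion, so its PD-1 is free of drug. Under the main schedule the later samples are drawn during pembrolizumab or soon after it. If the staining antibody needs the site that the drug occupies, or the drug hides its epitope, the CD279 signal falls because the receptor is covered. Such an error would be absent at baseline and present afterwards, so the paired difference would not cancel it. It would also point the way the one-sided test counts as success.

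The trial has a single arm, so no comparison group would show the artefact. The protocol recognises the general problem elsewhere: in 2.3.1 (Immunogenicity) it says "Trough levels of pembrolizumab interfere with the electrochemiluminescent (ECL) assay results", and the data cited there were limited to patients with low drug concentrations. No similar precaution is written for the PD-1 stain. At stake is whether a fall in CD279 could be read as immune restoration when it might be only receptor coverage.

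**Working it through.** **1. The plan's own figure.** For a paired t-test with n = 25 (24 df) and one-sided alpha 0.05, the critical value is 1.711. Power = P(T > 1.711), where T is noncentral t with noncentrality d√n. At d = 0.60, d√n = 3.0 and power is 0.898; 90% power needs d = 0.603. The stated 0.60 is therefore reproduced at about 90% power, which is inferred because 10.2.2 gives no power for this test. The sample size is not at fault.

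**2. CD279 tested alone, no true change.** Let s be the apparent drop caused by masking, in SDs of the paired difference. The documents give no value for s, so the range is an assumption. The chance of declaring a decrease is the same power function with d = s.

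| s | n = 25 | n = 16 |
|---|---|---|
| 0 (reagent does not compete) | 5% | 5% |
| 0.2 | 25% | 19% |
| 0.4 | 62% | 45% |
| 0.6 | 90% | 74% |
| 1.0 | 99.9% | 98% |

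The n = 16 column is the first-stage size in 10.2.1. It also shows the effect of missing end samples, since 7.1.13 makes the draw discretionary after early termination.

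**3. Eight markers averaged equally.** Assume standardised changes with common correlation ρ and an artefact in CD279 only. The shift of the mean is s/8, its SD is √((1 + 7ρ)/8), and d is their ratio. For s = 1.0 and ρ = 0: d = 0.125/0.354 = 0.354. With n = 25:

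| s | ρ = 0 | ρ = 0.3 | ρ = 0.6 |
|---|---|---|---|
| 0.2 | 10% | 7% | 7% |
| 0.6 | 27% | 14% | 12% |
| 1.0 | 53% | 25% | 19% |

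**4. Any one of eight markers suffices.** Assuming independence, the chance of at least one false decrease with no artefact is 1 − 0.95⁸ = 34%. With s = 0.6 in CD279 it is 1 − (1 − 0.898) × 0.95⁷ = 93%.

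**5. Time from last pembrolizumab to the end sample.** The sections disagree:

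- 10.2.2 with 7.3.7: week 52 is 1 week after a week-51 infusion.
- 7.3.7 footnote 2 with 7.3.2.11: ibrutinib runs 3 weeks past week 51 and the visit is 0 to 7 days after the last dose, so 3 to 4 weeks.
- 4.1: 54 weeks of ibrutinib from week 6 ends at week 60, or 9 weeks after week 51. The same section allows pembrolizumab to be extended up to 2 years, in which case drug could still be given at the draw.
- 7.3.2.10 names only ibrutinib for the visits after week 24. Read literally, the last infusion is at week 24, which is 28 weeks before week 52.

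The intermediate draws carry drug under either sampling list: 6 and 21, or 9 and 12, all fall within the 3-weekly infusions. They enter the exploratory paired and longitudinal analyses in 10.2.4, not the test in 10.2.2.

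**6. With CD279 left out.** n = 25, d = 0.60 and power 0.898 per test are unchanged. Under the any-marker reading, the no-artefact error becomes 1 − 0.95⁷ = 30%.

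**The case against.** The strongest objection is that masking depends on a fact the documents do not give. A detection antibody that does not compete with pembrolizumab would leave CD279 readable, and the choice may be recorded in a laboratory manual. The interference statement in 2.3.1 concerns an anti-drug-antibody assay; it shows that drug is present at trough, not that flow staining is affected. All of this stands. A reader might infer that the endpoint is biased by the drug. The documents do not support that; they support only that it can be, and that the plan states no safeguard.

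A reader might also infer that CD279 is certain to be counted in the tested endpoint, or that false-positive rates of 25% to 99.9% apply to the endpoint as a whole. Neither follows. Section 4.1 says the markers are tracked, 10.2.2 does not say which of them are tested or how, and those rates hold only for CD279 tested alone at n = 25.

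Finally, this is one component of one secondary endpoint. The go/no-go rule in 10.2.1 uses complete response alone, 10.2.4 describes the correlative work as largely exploratory, and T-cell activation and cytotoxic activity are measured separately by STAT phosphorylation and CD107a. That limits the consequence, but 10.2.2 still attaches a one-sided significance test to exhaustion markers.

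**Conclusion.** The concern holds as a conditional one. The plan lists the drug's own target among its exhaustion markers, compares a drug-free sample with one taken at about the end of pembrolizumab, tests in the direction masking would produce, and has neither a control arm nor a stated assay safeguard. If the reagent competes, the false-decrease rate for CD279 tested alone at n = 25 rises from 5% to between 25% and 90% for assumed drops of 0.2 to 0.6 SD. An equal-weight average of eight markers dilutes the artefact, to 7% to 53% for drops of 0.2 to 1.0 SD.

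These figures rest on assumed masking, on correlations not in the documents, and on a combination rule the plan does not state. That CD279 is PD-1 is standard nomenclature; the documents do not spell it out. Exposure in the end sample rests on the main schedule in 7.3.7 and is less certain if 7.3.2.10 is read literally. A wording change before analysis is worthwhile.

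**What to change.** In 4.1 and 10.2.2, exclude CD279 from the markers used to test for decreased T-cell exhaustion and report it descriptively or as receptor occupancy. If the laboratory documents a detection reagent shown not to compete with pembrolizumab, name it in 4.1, keep CD279, and add a sensitivity analysis without it.

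The same edit to 10.2.2 should state which markers are tested and how they are combined, because the size of the problem depends on that.

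Reconcile three sets of statements: the correlative draw weeks (7.1.13 and 7.3.7 against 7.2); the timing of the end sample (4.1, 7.3.2.11, 7.3.7 and 10.2.2); and whether pembrolizumab is given after week 24 (7.3.2.10 against 7.3.7).

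Exclusion costs one marker in the endpoint and a change of wording; the sample size and the 0.60 SD detectable effect stay as they are. Retention costs the laboratory's evidence of non-competition and one extra analysis.

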4.2.2 SECONDARY ENDPOINTS

1. Overall response rate (ORR) [CR + PR]
2. Restoration of immune response as measured by:

- a. Decreased markers of T-cell exhaustion
- b. Increased of quantitative immunoglobulin levels and subtype
- 2. Safety and toxicity of the combination
- 3. Progression free survival (PFS)
- 4. Incidence of Richter's transformation

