6.1.5 DOSING AND ADMINISTRATION

IBRUTINIB

Ibrutinib will be administered orally once daily at approximately the same time each day at the dose of 420

mg daily (3 capsules of 140 mg daily). Capsules will be swallowed whole with water. Capsules shall not be opened, broken or chew.

PEMBROLIZUMAB

Pembrolizumab will be administered intravenously at 200 mg every 3 weeks

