6.1.9 DURATION OF THERAPY

The duration of ibrutinib therapy will be up to 51 weeks.

The duration of therapy of pembrolizumab will be up to 51 weeks. Pembrolizumab dosing could be extended for up to 2 years if clinical benefit per investigator.

Patients will be considered evaluable if they complete at least 9 weeks or three infusions of pembrolizumab.

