² Pembrolizumab infusions will be every 3 weeks (+/- 3 days) for 51 weeks. Ibrutinib will be dispensed every 3 weeks on the day of the pembrolizumab infusion. The last dispensing of ibrutinib will occur at week 51 and dosing will continue for an additional 3 weeks. A pill diary will be provided to participants with every dispensing of ibrutinib supply. Pill diary from previous dispensing will be reviewed for accountability.

³ Serum pregnancy test will be performed on females of childbearing potential (FCBP). A FCBP is considered when a sexually mature female: 1) has not undergone a hysterectomy or bilateral oophorectomy; or 2) has not been naturally postmenopausal for at least 12 consecutive months.

⁴ Hematology will consist of CBC and differential with platelet counts. CBC/differential will be performed at day 1, week 0,1,2 after starting pembrolizumab and then weekly for the first month on ibrutinib (weeks 6, 7, 8, 9, 10). Starting at week 12, CBC/diff will be performed on days of the clinic visits for physical examinations/drug administration. Further CBCs with differential will be performed per physician discretion.

⁵ CMP includes: sodium, potassium, chloride, CO2, calcium, BUN, creatinine, glucose, albumin, total protein, alkaline phosphatase, total bilirubin, AST/SGOT, ALT/SGPT, LDH. Subjects will have CMP , week 0, 1, 2 after starting pembrolizumab and then weekly for the first month on ibrutinib (weeks 6, 7, 8, 9, 10). Starting at week 12, CMP will be performed on days of the clinic visits for physical examinations/drug administration. Further CMPs will be performed per investigator discretion.

⁶ TLS (tumor lysis syndrome) laboratory assessment will include: BUN, creatinine, phosphorus, potassium, LDH, uric acid. TLS laboratory evaluation will occur at days 1-3 of week 0 weeks 1 and 2 after starting pembrolizumab and then weekly for the first month on ibrutinib (weeks 6, 7, 8, 9, 10). Further TLS assessments will depend on clinical condition and/or at investigator discretion.

⁷ Peripheral blood samples for ZAP-70, IgVH mutational status, and FISH testing will be done ONLY if not ever performed. Previous results must be available in the medical record for determination of eligibility.

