10.2.2 ANALYSIS OF THE SECONDARY ENDPOINT(S)

1. Change in T cell exhaustion and/or inhibition following treatment
2. Change in serum immunoglobulin levels following treatment
3. Progression free survival (PFS) and association with immune biomarkers

To determine if T cell exhaustion or inhibition have change due to treatment with the combination therapy at baseline immune testing to immune testing following completion of pembrolizumab and ibrutinib treatments (week 52) using paired t-tests with the null hypothesis being that there is no change in immune measurements following treatment (i.e., $H_0: \mu_d = 0$). If the assumptions of normality do not hold upon assessment, we will instead use nonparametric t-tests (i.e., Wilcoxon Sign Rank Test). Similar tests will be used to determine if changes in serum immunoglobulin levels also resulted following treatment. Tests will be one-sided as based on biology expect the change in immune response to be in one direction following treatment. Tests will be considered statistically significant if the p-value is less than 0.05. Assuming the study go on to stage II and enroll 25 patients, we will be able to detect a modest effect size of 0.60. To determine the association of progression free survival (PFS) with immune biomarkers (T cell exhaustion and/or inhibition, serum immunoglobulin levels), Cox proportional hazards models will be fit with assumption of proportional hazards (PH) assumption check via Schoenfeld residuals. If the PH assumption does not hold, we will rely on use of non-parametric methods (Kaplan-Meier curve with log-rank tests) where the biomarkers will be dichotomized for analysis based on an optimal cut-point determination based on an outcome-oriented approach outlined by Contral and O'Quigley (Contal C, O'Quigley J. An application of changepoint methods in studying the effect of age on survival in breast cancer. Computational Statistics & Data Analysis. 1999;30:253-70.). A Cox regression of the log hazard ratio on the continuous biomarker (assuming a standard deviation of 1 and an anticipated event rate of 0.50) will have 80% power at a 0.05 significance level to detect a regression coefficient equal to 0.79 (i.e., hazard ratio of 2.20).

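### Pembrolizumab is itself an IgG4 antibody, so unless the subtyping ELISA is shown not to detect it, infused drug shifts the IgG4 part of the immune-restoration endpoint upward

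*Combined protocol and SAP*

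**What the plan says.** Drug: section 2.1 describes pembrolizumab as a "humanized monoclonal antibody (mAb) of the IgG4/kappa isotype". Section 6.1.2 repeats it: "Pembrolizumab is an IgG4 kappa immunoglobulin with an approximate molecular weight of 149 kDa".

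Dose and duration: section 6.1.5 states "Pembrolizumab will be administered intravenously at 200 mg every 3 weeks". Footnote 2 of section 7.3.7 states "Pembrolizumab infusions will be every 3 weeks (+/- 3 days) for 51 weeks". Section 6.1.9 adds that "Pembrolizumab dosing could be extended for up to 2 years if clinical benefit per investigator".

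Assay and endpoint: section 4.1 (Biomarker Research, item 3) states "Humoral immunity will be monitored in terms of quantitative serum immunoglobulin levels as well as IgG subtyping by ELISA assay". Section 4.2.2, under restoration of immune response, lists "Increased of quantitative immunoglobulin levels and subtype". The Study Summary's endpoint list words this item as improved levels only and does not mention subtype. Section 3 also lists subtyping among the exploratory objectives.

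Sampling: section 7.1.13 and footnote 12 of section 7.3.7 give a pre-dose baseline, week 6, week 21 and end of ibrutinib. Section 7.2 gives weeks 9 and 12 in place of 6 and 21.

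Analysis: section 10.2.2 compares T-cell measures at baseline and after treatment (week 52) by a paired t-test or Wilcoxon signed-rank test, one-sided at 0.05. It continues: "Similar tests will be used to determine if changes in serum immunoglobulin levels also resulted following treatment". Section 10.2.4 plans paired t-tests and mixed models over all four time points.

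**The concern.** A subclass ELISA commonly identifies IgG4 by the constant region of its heavy chain, which a humanized IgG4 drug shares. The plan names no reagent and no drug-tolerance check, so nothing in it rules out that infused pembrolizumab is counted as the patient's own IgG4. Baseline has no drug and the later scheduled samples may have some, so the paired difference would contain the drug concentration. That pushes in the direction the plan counts as restoration.

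An IgG4 rise that is partly or wholly drug could then be reported as recovered humoral immunity. With no control arm, the artefact would look the same as the hypothesised effect. The protocol recognises this kind of problem elsewhere: the immunogenicity paragraph of section 2.3.1 says trough pembrolizumab disturbs the anti-drug-antibody assay. It does not carry the point over to the subtyping ELISA.

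**Working it through.** **1. The plan's own figure.** Section 10.2.2 gives a detectable effect size of 0.60 with 25 patients and does not state the power. For a one-sided paired t-test at 0.05: df = 24, noncentrality = 0.60 x sqrt(25) = 3.0, power = 0.898. The effect detectable with 90% power is 0.603. The stated figure is therefore a one-sided 0.05 test with about 90% power, and the same test is used in step 4.

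**2. Timing.** Dosing every 3 weeks from week 0 to week 51 gives 51/3 + 1 = 18 infusions, or 18 x 200 = 3,600 mg if all are given. The final sample depends on which section is followed:
- Week 52 (10.2.2), or week 54 (footnote 2 of 7.3.7: last dispensing at week 51 plus 3 weeks). The end-of-treatment window of up to 7 days extends the latter to week 55.
- Counting ibrutinib from its week-6 start: 51 weeks (6.1.9) ends at week 57, 12 months (7.3.2.4) at about week 58, and 54 weeks (4.1) at week 60.
- Section 7.3.2.10 lists only ibrutinib as study drug at the visits from week 24 to 51. Sections 4.1, 6.1.9 and 7.3.7 give pembrolizumab to week 51.

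**3. Drug concentration.** The documents give no pharmacokinetics. Assumed: one compartment, volume V = 3.5-6 L, half-life 14-26 days. C(t) = (200/V) x sum over doses of exp(-k x days since dose), with k = ln 2 / half-life.
- Highest case, week 52: 200/3.5 = 57.1; accumulation over 18 doses 2.33; decay over 7 days 0.830; product 111 mcg/mL.
- Lowest case, week 52: 200/6 = 33.3; accumulation 1.55; decay 0.707; product 36 mcg/mL.

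| Sample | Drug IgG4, mcg/mL |
|---|---|
| Week 6, pre-dose | 16-51 |
| Week 21, pre-dose | 18-75 |
| Week 52, last dose week 51 | 36-111 |
| Week 54 | 18-76 |
| Week 55 | 13-63 |
| Week 57 | 6-44 |
| Week 58 | 5-36 |
| Week 60 | 2-25 |
| Week 52, last dose week 24 | under 1 |

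**4. Effect on the test.** Suppose the patient's own IgG4 does not change and the drug adds a constant shift of s SDs of the paired change. The rejection probability comes from the noncentral t distribution with df = 24 and noncentrality 5s:

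| s | Probability of a significant rise |
|---|---|
| 0 | 0.05 |
| 0.1 | 0.12 |
| 0.2 | 0.25 |
| 0.4 | 0.62 |

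The SD of the paired change is not in the documents. As an illustration, a 40 mcg/mL shift is 0.4 SD if that SD is 100 mcg/mL (probability 0.62) and 0.2 SD if it is 200 mcg/mL (0.25). A 10 mcg/mL shift is 0.1 SD at an SD of 100 mcg/mL (0.12).

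**5. Other measures.** For an assumed total IgG of 3-10 g/L, the 13-111 mcg/mL range is between 0.013/10 = 0.13% and 0.111/3 = 3.7%. The drug adds nothing to IgG1-IgG3, IgA or IgM.

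**The case against.** The strongest reply is that the plan never specifies a one-sided test of IgG4. Section 10.2.2 names only serum immunoglobulin levels, the Study Summary's endpoint omits subtype, subtyping also appears as exploratory, and section 10.2.4 states no one-sided direction. This stands: applying the one-sided test to IgG4 is a reading of the plan. It is a natural one, because subtype is written into the section 4.2.2 endpoint and no other test is given for it there.

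The timing also cuts both ways. A final sample at weeks 57-60 carries much less drug than one at week 52, and if pembrolizumab ended at week 24 the baseline-to-end contrast is almost clean. The week 6 and week 21 samples in the section 10.2.4 analyses would still be affected. The possible extension to 2 years works in the other direction for some patients.

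A reader might infer that the IgG4 reading must rise whatever the treatment does, or that the assay cannot separate drug from patient antibody. The documents support neither. The reagent is unspecified, and a fall in the patient's own IgG4 could offset the added drug. Nor do they support extending the criticism to total IgG or the other classes.

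Finally, no stopping rule or go/no-go decision uses this measure; those rest on complete response and toxicity.

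**Conclusion.** The point holds as a bias of clear direction and uncertain size, limited to one IgG subclass within one part of a secondary endpoint and the related exploratory analyses. That pembrolizumab is IgG4, that baseline is drug-free, that a rise counts as success, and that there is no exclusion or correction all come from the documents. That the ELISA reads the drug is inferred from how subclass assays usually work.

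The concentrations rest on assumed pharmacokinetics and on which schedule is followed: about 13-111 mcg/mL, about 2-44 mcg/mL, or under 1 mcg/mL at the final sample. The error rates of about 0.12, 0.25 and 0.62 are exact for shifts of 0.1, 0.2 and 0.4 SD under a paired t-test with 25 patients. Which shift applies cannot be settled from the documents, because they give neither baseline IgG4 nor the SD of change. It is worth correcting because the correction is cheap and the data alone would not reveal the problem.

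**What to change.** In sections 4.1, 4.2.2 and 10.2.2:
- Leave IgG4 out of the immune-restoration endpoint for any sample taken with pembrolizumab on board.
- Base the subtype claim on IgG1-IgG3, with IgA and IgM for levels, and state which test applies to subtype.
- Report IgG4 descriptively, labelled as including drug, unless the assay is shown not to detect pembrolizumab. Apply the same rule to the on-treatment samples in section 10.2.4.

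Separately, reconcile the pembrolizumab and ibrutinib duration statements (4.1, 6.1.9, 7.3.2.4, 7.3.2.10, and 7.3.7 with its footnote 2) and the sampling weeks (7.1.13 and footnote 12 of 7.3.7 against 7.2), because they determine how much drug the final and interim samples contain.

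The cost is protocol and SAP wording, with no new samples or visits. The downside is that one of the four IgG subclasses no longer counts as evidence of restoration.
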